Statistical Analysis Plan

December 21st, 2023

NCT01817166

PHRC-N/2012/ET-01

Efficacy of Cholecalciferol (Vitamin D3) for Delaying the Diagnosis of MS After a Clinically Isolated Syndrome

Final detailed statistical analysis plan drafted before data lock and before the commencement of statistical analyses.

An initial data analysis will provide a description of each arm. Statistical results will be presented using mean and standard deviation for quantitative variables with a Gaussian distribution, and median and interquartile range for other quantitative variables. For qualitative variables, frequencies and associated percentages will be presented.

Demographic, clinical (initial relapse), radiological (diagnostic MRI), and biological (lumbar puncture, vitamin D) data will be described. In particular, it will be determined for each patient whether the diagnostic criteria of McDonald 2017 are met at inclusion (Thompson et al., 2018).

The statistical analysis will be conducted by the BESPIM of the CHU de Nîmes using R 4.1.1 or a later version (R Core Team (2021). R Foundation for Statistical Computing, Vienna, Austria).

Primary Analysis (Rate of EDA)

The primary objective is to assess the efficacy and tolerance over 2 years of treatment with Cholecalciferol (Vitamin D3) in patients who have experienced a clinically isolated syndrome at high risk of multiple sclerosis (CIS, according to the McDonald criteria of 2005). This efficacy will be measured by comparing the risk of conversion to relapsing-remitting multiple sclerosis (RRMS) within 2 years after CIS, according to 2005 McDonald criteria (new lesions on follow-up brain and spinal cord MRIs or new relapses) (McDonald et al., 2001; Polman et al., 2005), between the arm receiving Cholecalciferol and the arm receiving the placebo.

Following the actual diagnostic criteria for MS (McDonald 2017), most patients present with a diagnosis of active MS and conversion corresponds to the current concept of EDA (evidence of disease activity defined by clinical relapses or imaging (gadolinium-enhancing lesions or new or unequivocally enlarging T2/FLAIR lesions) (Lublin et al., 2013) an "no conversion" corresponds to NEDA (no evidence of disease activity). Hence, the event will be the occurrence of EDA within the two years of follow-up (relapse and/or appearance of new or enlarging lesions (NEL) on follow-up MRIs at 3, 12, and 24 months).

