Secondary Objective A: Evaluate clinical efficacy on the number of relapses during the study period. The determination of the number of relapses is based on data from the EDA visit and the summary table of relapses based on the evaluation at Month 24. The number of relapses will be compared between the two arms using a non-parametric Mann-Whitney Wilcoxon test.

Secondary Objective B1: Describe the parameters of magnetic resonance imaging (brain and spinal cord MRI) at the "conversion MRI":

- Appearance of NEL on brain MRI in T2/FLAIR (including size increase) and/or on spinal cord MRI in T2 ("conversion MRI" Yes/No)

- New brain or spinal cord gadolinium-enhancing T1 lesions (active lesion(s) Yes/No)

- Lesion load in mm³ of each brain MRI from the FLAIR sequence

- Total number of gadolinium-enhancing T1 lesions (categorical measure: none, one, at least two)

Secondary Objective B2: Describe the magnetic resonance imaging (brain and spinal cord MRI) parameters during follow-up:

Normalized brain volume obtained from the 3D T1 sequence at different visits
Change in global brain volume (mm3, from the 3D T1 sequence) between the baseline examination and the 2-year examination on one hand, and between the 3-month examination and the 2-year examination on the other hand, to limit the effect of pseudo-atrophy after the first relapse

Secondary Objective C: Evaluate efficacy on disability progression, measured by the EDSS score and Kurtzke functional scores (Kurtzke 1983; Noseworthy et al. 1990; Goodkin et al. 1992) at baseline and during follow-up, then considering scores at M0 and M24 only.

Secondary Objective D: Evaluate efficacy on cognitive abilities (PASAT) (Cutter et al. 1999; Fischer et al. 1999; Parmenter et al. 2006) at baseline and during follow-up, then considering scores at M0 and M24 only.

Secondary Objective E: Evaluate efficacy on quality of life (EQ5D, SF36, TLS-QoL10, and TLS-COPING10 questionnaires), fatigue (FSMC questionnaire), and anxiety/depression (HADS questionnaire) at baseline and during follow-up, then considering scores at M0 and M24 only.

For Objectives C, D, and E:

- A first mixed-effects regression model will be used to compare the evolution of the outcome measures (EDSS score for Objective C, PASAT score for Objective D, and quality of life scores for Objective E). The model variables will include:
 - Scores at different visits (outcome variables)

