 - Treatment arm (explanatory variable of interest)
 - Center as a random effect (multiple patients per center)
 - Patient as a random effect (multiple measurements per patient)
 - Visit (temporal chronological variable)
 - Interaction between the treatment arm and the presence of a relapse during follow-

up

- A second mixed-effects regression model will be used to compare the M24 scores of the outcome measures while adjusting for baseline scores (M0):
 - M24 score (outcome variables)
 - Treatment arm (explanatory variable of interest)
 - Center as a random effect (multiple patients per center)
 - M0 score (adjustment variable)

- Interaction between the treatment arm and the presence of a relapse during follow-up

Secondary Objective F: Evaluate treatment tolerance on:

a. The occurrence of AEs and SAEs

- b. Pharmacological measurement of serum concentrations of 25(OH)D2 and 25(OH)D3
- c. Measurement of serum calcium, urinary calcium, and renal function

The number of AEs and SAEs per patient will be described by arm.

For points b and c, a mixed-effects regression model will be used to compare the evolution of measurements during follow-up. The model variables will include:

- Measurements at different visits (outcome variable)
- Treatment arm (explanatory variable of interest)
- Center as a random effect (multiple patients per center)
- Patient as a random effect (multiple measurements per patient)
- Visit (temporal chronological variable)

Secondary Objective G: Initial formulation: Correlate the variation in clinical and imaging parameters with the initial level and changes in the levels of 25(OH)D2 and 25(OH)D3 under treatment.

Reformulated Objective G1: Study the link between the severity of impairment (parameters measured by the baseline MRI, such as the number of lesions, EDSS score) and the vitamin D level measured during pre-screening (25(OH)D2 and 25(OH)D3).

A mixed-effects regression model will be estimated. The model variables will include: - Severity of impairment at inclusion (outcome variable). Several variables will be successively modeled: binary variables for MRI parameters (using a logistic regression model) and a quantitative variable for the EDSS score.

- Levels of 25(OH)D2 and 25(OH)D3 at pre-inclusion (explanatory variables of interest)
- Treatment arm (adjustment variable)
- Center as a random effect (multiple patients per center)

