baseline MRI scan for that patient if known. If the latter is also missing, the gadoliniumenhancement status used as the randomization stratification variable will be employed.

- When the date of the CIS is missing, it will be extrapolated from the date of the diagnostic MRI scan plus the median time between the CIS and the diagnostic MRI scan.

If the number of T2/FLAIR lesions (used as an indicator of lesion burden, in two categories "<9 lesions " and " >= 9 lesions ") at the baseline MRI is missing, it will be analyzed in a third category "Number of Lesions Missing".

- If the EDSS score is missing at baseline, it will be imputed by the first non-missing EDSS scores at the M3 and M12 visits, subtracting the median of the EDSS score difference between M0 and M3 (respectively between M0 and M12) obtained from patients with scores recorded at both visits. If the result is negative, the median will not be subtracted.

For other secondary outcome measures, no method for imputing missing data is planned.

Analysis population:

Patients who did not receive the study treatment will not be considered in the analyses, which will be conducted on a modified intention-to-treat basis.

All patients who received at least one dose of the study treatment will be included in the analyses.

Thus, the following individuals will not be considered in the analyses:

- Patients with "Study discontinuation at the investigator's decision due to disease activity identified on the baseline MRI" or occurrence of a relapse before treatment onset.

- Patients who withdrew their consent.

- Patients who did not undergo a baseline MRI (withdrawal of consent, inability to undergo MRI).

- Patients lost to follow-up immediately after inclusion (at the inclusion visit and/or baseline MRI), with no follow-up data.

- Patients mistakenly included without MS or with occurrence of a relapse before the baseline MRI.

These patients cannot be included in an intention-to-treat analysis because they have no follow-up and, therefore, no information on disease activity during follow-up.

Bibliographic References

Edgar et al 2021 : Including random centre effects in design, analysis and presentation of multi-centre trials. Trials. 2021, 22:357.

Kahan 2014 : Accounting for centre-effects in multicentre trials with a binary outcome – when, why, and how? BMC Medical Research Methodology, 2014, 14:20.

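### Objectives C to E: the model meant to compare evolution between arms has no arm-by-visit term, and both models interact arm with relapse, itself a trial outcome

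*SAP*

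**What the plan says.** All references are to the SAP, Secondary Analyses, unless stated.

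- **Model 1, Objectives C, D and E.** The purpose is given as: "A first mixed-effects regression model will be used to compare the evolution of the outcome measures". Objectives C, D and E each take the scores "at baseline and during follow-up, then considering scores at M0 and M24 only", so M0 is one of the response times. The listed terms are arm (named as the variable of interest), random center, random patient, visit, and "Interaction between the treatment arm and the presence of a relapse during follow- up". There is no arm-by-visit term.
- **Model 2, same objectives.** The M24 score is modelled on arm, M0 score and random center, with the same arm-by-relapse interaction.
- **Neither model** lists a relapse main effect, says how relapse is coded, or names the contrast that is the treatment comparison.
- **Relapse elsewhere.** It is the outcome of Objective A: "The number of relapses will be compared between the two arms using a non-parametric Mann-Whitney Wilcoxon test". It is also a component of the primary outcome (Primary Analysis, Rate of EDA): "the event will be the occurrence of EDA within the two years of follow-up (relapse and/or appearance of new or enlarging lesions".
- **Objective F, points b and c.** "For points b and c, a mixed-effects regression model will be used to compare the evolution of measurements during follow-up". The listed terms again include arm and visit but not their interaction. The SAP does not say whether baseline is among the outcomes here.

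**The concern.** There are two separate faults.

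**No arm-by-visit term in model 1.** With arm and visit as main effects only, the fitted arm profiles are forced to be parallel, so no coefficient measures a difference in evolution. Because M0 is among the responses and randomisation makes the expected M0 difference zero, the arm coefficient is also pulled towards zero. Model 2 has a single outcome time and needs no such term.

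**Arm by relapse in both models.** Relapse during follow-up happens after randomisation, and treatment may change it. Once it is in the model with no/yes coding, the arm coefficient describes relapse-free patients, a group that randomisation did not form. Benefit that works by preventing relapses is left out. If treatment changes relapse risk, and relapse and score share causes, the remaining contrast is biased.

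The stake is that objectives framed as efficacy on disability, cognition and quality of life would be answered by coefficients that are not the randomised comparison.

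**Working it through.** The SAP gives no effect size or power for Objectives C to E, so there is no figure of its own to reproduce.

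**Inputs from the SAP**
- EDSS visits M0 and M24 (Objective C), and M3 and M12 from the missing-data section: "it will be imputed by the first non-missing EDSS scores at the M3 and M12 visits".
- 316 patients (Primary Analysis, Rate of EDA).
- Significance level 0.05.

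**Inputs assumed**
- Equal split, 158 per arm. The sample size cancels in the power comparisons below.
- Within-patient correlation ρ of 0.5 to 0.8, unit SD, random patient intercept.
- The dropout, relapse proportions and effect shapes stated below.

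**1. What the model 1 arm coefficient estimates (relapse terms set aside)**

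With balanced visits it is the mean of the visit-specific arm differences. As a share of the M24 effect:
- Constant after baseline: (0+1+1+1)/4 = 0.75.
- Linear growth to M24: (0+3+12+24)/(4×24) = 0.41.

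The visits for the other scores are not given. With M0 and M24 only, both shares are 0.50. With M0, M12 and M24 they are 2/3 = 0.67 and (0+0.5+1)/3 = 0.50.

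With dropout, let δ_j be the difference at visit j, and let π_k be the share of patients with their first k visits. Then

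coefficient = Σ π_k (δ_1+…+δ_k)/(1−ρ+kρ) ÷ Σ π_k k/(1−ρ+kρ).

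Take ρ = 0.7, with 80% complete, 10% seen to M12 and 10% seen to M3. The divisors are 3.1, 2.4 and 1.7.
- Denominator: 0.8×4/3.1 + 0.1×3/2.4 + 0.1×2/1.7 = 1.275.
- Constant: (0.8×3/3.1 + 0.1×2/2.4 + 0.1×1/1.7)/1.275 = 0.916/1.275 = 0.72.
- Linear: (0.8×1.625/3.1 + 0.1×0.625/2.4 + 0.1×0.125/1.7)/1.275 = 0.453/1.275 = 0.36.

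**2. Power of that coefficient**

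Take an effect d that M24 adjusted for M0 detects with 80% power: d = 2.80·√(2(1−ρ²)/n). The SE of the model 1 arm term is √(2(ρ+(1−ρ)/4)/n). The noncentrality is share × d/SE. For ρ = 0.5 and a constant effect this is 0.75 × 2.80 × √(0.75/0.625) = 2.30, which gives 63%.

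| ρ | constant | linear |
|---|---|---|
| 0.5 | 63% | 24% |
| 0.6 | 52% | 19% |
| 0.7 | 40% | 15% |
| 0.8 | 28% | 12% |

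**3. Cost of the relapse interaction in model 2**

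With relapse coded no/yes and its main effect included, only the (1−p)n relapse-free patients per arm inform the arm coefficient. Its variance is multiplied by 1/(1−p), and the noncentrality becomes 2.80·√(1−p). The simulation column used 4,000 trials, ρ = 0.7 and relapse independent of arm and score.

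| p | formula | simulation | simulation without relapse terms |
|---|---|---|---|
| 20% | 71% | 70.8% | 80.0% |
| 30% | 65% | 64.4% | 80.2% |
| 40% | 58% | 57.7% | 79.2% |

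**4. Benefit left out**

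Suppose treatment acts only by cutting relapse from 40% to 30%, each relapse adds 0.5 EDSS points at M24, and nothing else links the two. The total effect is (0.30−0.40)×0.5 = −0.05. The expected arm coefficient given relapse is 0.

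**5. Bias**

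A simulation of 2,000,000 patients used 33% relapse on control, no direct treatment effect, and an unmeasured severity factor raising both relapse and score (unit-SD baseline, residual SD 0.8). When treatment lowered relapse to 24%, the arm contrast in relapse-free patients was about +0.03. At 18% relapse it was +0.04 to +0.05. The true direct effect was 0 and the total effect was 0 or negative, so the sign can reverse. With relapse equal in both arms the bias was about 0.

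**6. The list fitted literally**

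With relapse as a numeric 0/1 variable and no main effect, the arm coefficient compares relapse-free treated patients with all controls. If treatment does nothing, 33% relapse and relapse adds 0.5, its expected value is −0.33×0.5 ≈ −0.17 instead of 0.

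**The case against.** - **The power loss in step 3 depends on the contrast read off the model.** The SAP fixes no coding and no contrast. An arm effect averaged over the observed relapse proportions of the same fitted model keeps about 80% power in simulation. This stands: 71%, 65% and 58% belong to the no/yes-coded arm coefficient. Averaging still conditions on a post-randomisation event, so it restores precision but not the randomised comparison.
- **No relapse main effect is listed, so step 3 assumes a term the SAP does not name.** True, but a literal numeric fit is worse (step 6). Some software codings absorb the main effect and avoid this; the SAP does not say which applies.
- **The model 1 power figures omit the relapse term that model 1 contains.** True. They isolate the first fault and are not predictions for the full model.
- **Step 4 shows a different estimand, not bias, and the effect is tiny.** Correct: 0 is the right direct effect there, and bias also needs shared causes (step 5). A total effect of −0.05 would have only about 8% to 14% power even in the corrected model 2 (assumed SD 0.7 to 1.3, ρ = 0.7). The example shows what is left out, not a likely loss.
- **The list of terms may not be exhaustive, and model 2 already compares M24 adjusted for M0.** A final plan that leaves open the one term that answers its question has not prespecified it. Model 2 does limit the dilution to one of two analyses, but it carries the same relapse interaction.

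**Conclusion.** The concern holds, and should be fixed. As listed, model 1 for Objectives C to E cannot test a difference in evolution. Its arm coefficient captures 75% (constant) or 41% (linear) of the M24 effect for EDSS on a balanced M0/M3/M12/M24 schedule, or 72% and 36% with the assumed dropout. Both models condition on relapse, and no version without it is planned, so these objectives have no randomised comparison.

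The specification faults rest on the text alone; the power and bias figures rest on the assumptions stated with them. If treatment affects neither relapse nor score and the relapse main effect is included, type I error stays nominal. Objective F, points b and c, shares the missing arm-by-visit term, but no dilution is claimed because its baseline handling is not stated. The primary EDA analyses and Objective A are unaffected.

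**What to change.** - **Model 1 (C to E):** add arm by visit with visit categorical, and name the arm difference in change from M0 as the contrast tested. Alternatively, model post-baseline visits only, with the M0 score as covariate.
- **Objective F, points b and c:** make the same change, and state whether baseline is an outcome.
- **Models 1 and 2 (C to E):** remove arm by relapse from the main analysis. Model 2 becomes the M24 score on arm, M0 score and random center.
- **If a split by relapse is wanted:** report it as descriptive, label it non-randomised, and include the relapse main effect.

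The cost is SAP wording and a changed model formula; the same data are used.

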Furthermore, the lesion load in FLAIR in mm³ (reference MRI) is available only for 258 out of 316 patients (those for whom the MRI images could be retrieved). Moreover, obtaining this volume is not reliable because the software does not provide a sufficiently precise estimate. Therefore, no adjustment will be made for the lesion load, and the number of T2/FLAIR lesions on the reference MRI will be used instead as an indicator of lesion load (in 2 modalities: <9 lesions, >= 9 lesions).

In the event of the use of an incorrect stratum during randomization (randomization performed for the stratum with contrast enhancement on the diagnostic MRI while the true value was an absence of contrast enhancement, and vice versa), the analyses will be adjusted for the contrast enhancement value on the diagnostic MRI (Yelland et al., 2022). The stratum error rate will be described by arm.

Primary Analysis (Time to EDA)

Time to EDA is the duration between the date of the first administration of the experimental treatment and the date of EDA.

Date of EDA is:

- The date of the "conversion MRI" for patients with EDA determined by the appearance of NEL on MRI without having a relapse during the follow-up,

- The date of the first symptoms of a relapse for patients with EDA determined by a new relapse without the appearance of NEL on MRI during the follow-up,

- The earlier of the two dates between the date of the first symptoms and the date of the MRI showing NEL for patients who have both a relapse and NEL on MRI during the follow-up.

Patients lost to follow-up or not showing EDA during the follow-up will be right-censored at the date of the last news. The endpoint date will be established for each patient at the date of the end-of-study visit conducted 24 months (2 years) after inclusion.

Time to EDA in both arms will be graphically represented using the Kaplan-Meier method.

The proportional risk of EDA in the experimental arm compared to the placebo arm will be estimated along with its 95% confidence interval using a random-effects Cox model (random center effect) after checking the proportional hazards assumption. Adjustment will be made for the same variables as those used when analyzing the rate of EDA.

Secondary Analyses

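### The only Month 24 arm contrast for EDSS, PASAT and quality of life rests on patients with a Month 24 score, and it is biased if leaving depends on interim worsening differently by arm

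*SAP*

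**What the plan says.** In the SAP section Secondary Analyses, each of Objectives C, D and E is assessed "at baseline and during follow-up, then considering scores at M0 and M24 only". Two models follow.

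- **Model 1** takes the scores at all visits. It lists arm, visit, centre and patient as random effects, and an interaction of arm with relapse during follow-up. No arm-by-visit term is listed.
- **Model 2** is introduced with "A second mixed-effects regression model will be used to compare the M24 scores of the outcome measures while adjusting for baseline scores". It lists the M24 score as outcome, with arm, random centre, the M0 score and the arm-by-relapse interaction. No interim score enters.

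On missing data, the SAP states: "For other secondary outcome measures, no method for imputing missing data is planned". The same section shows that interim EDSS exists, because a missing baseline EDSS is filled in from the "first non-missing EDSS scores at the M3 and M12 visits".

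The SAP expects some patients to leave early: "Patients lost to follow-up or not showing EDA during the follow-up will be right-censored at the date of the last news". For the EDA rate it also plans a maximum-bias sensitivity analysis. It plans nothing comparable for EDSS, PASAT or quality of life.

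**The concern.** Model 2 can use only patients with an M24 score. Suppose a patient worsens by Month 12 and then leaves. The worsening is on record, but the Month 24 comparison does not see it. Conditioning on M0 and arm is enough only if, given those two (and relapse, as listed), reaching Month 24 is unrelated to the scores in between.

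If that fails in one arm more than in the other, the arm whose worsening patients leave looks better than it is. If that is placebo, a real benefit shrinks. If it is the active arm, a benefit can appear where there is none.

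Model 1 does not fill the gap. Without an arm-by-visit term it has no Month 24 arm effect to report, and the SAP does not name it as a check on model 2. Nor can model 2 meet the Analysis population section, which says everyone who took at least one dose is analysed.

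**Working it through.** **No figure to reproduce.** The SAP gives no sample size, SD, correlation or dropout rate for these outcomes. Everything below except the 316 is an assumption, shown as a range.

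**Inputs**
- 316 patients (SAP, Primary Analysis, paragraph on lesion load). An equal split is assumed: 316 / 2 = 158 per arm.
- Scores at M0, M3, M12 and M24 in SD units, with lower meaning better (as for EDSS). Equal correlation ρ between visits, 0.5 or 0.7. No true effect.
- A share d leaves after M12. In one arm leaving depends on L = (M12 − M0)/√(2(1−ρ)) + 0.7 × standard normal noise, and the patients with the highest L leave. In the other arm leaving is random at the same rate.

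**Hand calculation of the model 2 bias**
1. Var(L) = 1 + 0.7² = 1.49.
2. Given M0, the M24 residual has covariance (ρ − ρ²)/√(2(1−ρ)) with L. Dividing by √1.49 = 1.2207 gives c. For ρ = 0.5, c = 0.25/1/1.2207 = 0.205. For ρ = 0.7, c = (0.21/0.7746)/1.2207 = 0.222.
3. Among those who stay, the mean of standardised L is −k, where k = φ(z)/(1−d) and z is the upper-d normal quantile. So k = 0.109, 0.195, 0.350 and 0.497 at d = 5, 10, 20 and 30%.
4. Bias ≈ −k × c. At d = 20% and ρ = 0.5: −0.350 × 0.205 = −0.072 SD.

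**Against simulation** (2,000 trials per setting, 158 per arm). Model 2 is fitted here without relapse terms. The longitudinal estimate keeps M3 and M12.

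| Leaving d | Hand, ρ = 0.5 / 0.7 | Simulated model 2, ρ = 0.5 / 0.7 | Model 2 rejection at nominal 5% | Longitudinal bias |
|---|---|---|---|---|
| 5% | −0.022 / −0.024 | −0.024 / −0.026 | 5.2% / 6.4% | −0.001 / −0.001 |
| 10% | −0.040 / −0.043 | −0.040 / −0.042 | 7.7% / 7.7% | 0.002 / 0.001 |
| 20% | −0.072 / −0.078 | −0.074 / −0.077 | 9.4% / 13.8% | 0.000 / 0.003 |
| 30% | −0.102 / −0.110 | −0.101 / −0.113 | 15.1% / 22.1% | 0.005 / 0.000 |

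When the other arm loses nobody, the results are similar: −0.075 / −0.081 at 20% and −0.106 / −0.112 at 30%, with rejection up to 24.0%.

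**A gentler leaving rule** (ρ = 0.6; log-odds of leaving 1.2 per SD of M0-to-M12 worsening, in placebo only). The bias is 0.013, 0.024, 0.047 and 0.070 SD at 5, 10, 20 and 30%. With a true effect of −0.30 SD and 20% leaving, model 2 has 71% power, against 84% when both arms follow the same rule.

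**In points.** Assume a 0.30-point effect, with placebo leaving depending on the M12 score (odds ratio 2.7 per point) and random leaving in the other arm. At 19% leaving, 11% to 30% of the effect is lost, depending on the SD assumed: 0.11 × 0.30 = 0.033 to 0.30 × 0.30 = 0.09 points. At 5-10% leaving, about 3% to 15% is lost.

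**With relapse and arm-by-relapse added** (ρ = 0.6, 35% relapsing). The arm coefficient is biased by −0.071 SD at 20% and −0.098 SD at 30%. Without those terms the same data give −0.090 and −0.126. The bias shrinks but stays.

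**Controls.** There is no bias beyond simulation noise (within 0.006 SD) when leaving is random, depends only on M0, or follows the same rule in both arms with no true effect. With a true effect of −0.30 SD and the same rule in both arms, the estimate is attenuated by 0.018, 0.024 and 0.031 SD at 10, 20 and 30%.

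**The case against.** The strongest reply is that the SAP does use the interim scores. Model 1 is listed first, takes every visit with a patient random effect, and is not ranked below model 2. That stands: a reader might infer that the plan throws the interim scores away, and it does not. But model 1 as listed estimates no Month 24 difference, so it cannot stand in for model 2 at that time point.

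Second, the harm needs leaving that differs by arm, and nothing in the SAP says that it does. The primary analysis section fixes each patient's endpoint date at the 24-month visit, and relapses are counted up to Month 24. This suggests that follow-up was meant to continue after disease activity. That also stands, and it makes the bias conditional. It does not rule dropout out, since the SAP writes rules for patients lost to follow-up.

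Third, a reader might infer that a third of a real effect would be lost. The documents give no dropout rate, SD or correlation to support one such figure. A loss near 30% arises only at the upper end of the assumptions, with about 19% leaving and strong dependence on the M12 score in one arm alone.

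Last, these are secondary outcomes. That is so, and it limits the weight of the point.

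**Conclusion.** The point holds in conditional form. The SAP's only Month 24 arm contrast for Objectives C, D and E uses patients with an M24 score and ignores what was recorded on those who left. If leaving depends on interim worsening differently by arm, that contrast is biased in favour of the arm whose worsening patients leave.

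Across the assumptions tried, the size is about 0.01 to 0.05 SD at 5-10% leaving, 0.04 to 0.08 SD at about 20%, and up to about 0.11 SD at 30%. It is small at the low end and begins to matter from about 20%. It is close to zero under random leaving or a common rule, apart from an attenuation of 0.02 to 0.03 SD when there is a true effect of 0.30 SD. The documents do not show that the Month 24 results will in fact be biased, because they report neither how many patients leave nor why.

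Interim visits are named only for EDSS. For PASAT and quality of life the SAP says that scores are taken during follow-up without naming the visits, so the gain there depends on what was collected. The primary EDA analysis is unaffected.

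**What to change.** - Take the main Month 24 contrast from one longitudinal model of all post-baseline scores: visit, arm by visit, M0 score by visit, unstructured within-patient covariance and random centre.
- Include every patient in either arm who received at least one dose and has at least one post-baseline score.
- Keep model 2 as a completer sensitivity analysis.
- Tabulate, by arm, the number without an M24 score and their last available score.

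Whether the relapse interaction belongs in these models is a separate question; this change is needed with or without it.

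The cost is SAP wording and slightly more modelling, on data already collected and with standard software. The SAP describes itself as drafted before data lock and analysis. The new estimate still assumes that the recorded scores explain leaving. That is weaker than what model 2 assumes, but it remains an assumption.
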